1.3 Roles of professionals in screening for undernutrition

In general, and more particularly in the Forcilles hospital, dieticians play a major role in detecting undernutrition (8,9). They ensure a prospective watch on the patient's admission to the hospital, with the collection of indicators related to BMI and weight loss, in collaboration with the nurses and care assistants. They also carry out a dietary consultation to clarify the above criteria, to evaluate the reduction of intake and absorption, in collaboration with the physician, and the realization of body composition measurements, such as bio-electrical impedanceometry. The evolution of the definition of undernutrition, with an important place in the muscular and functional evaluation of the patient, implies new actors: the physiotherapist and the Adapted Physical Activity Teacher (APAT). Indeed, they have expertise in the evaluation of the patient's muscular function and functional capacities. As part of their diagnostic assessment, the physiotherapist is used to evaluating muscle function by dynamometry (10), as well as the patient's functional capacities by field tests or the use of scores. The EAPA also participates in the performance of field tests.

The collaboration between dieticians, physiotherapists, EAPAs, nurses, care assistants and doctors thus makes it possible to meet the need to screen for undernutrition according to this new definition.

1.4 Assessment of muscle function

Physical therapists and EAPAs use different tools to assess different aspects of muscle function, such as strength or walking speed in more functional tests.

Isometric grip strength is strongly correlated with lower extremity muscle strength, and is a pejorative marker of mobility in weakness (7). It has been

observed a linear relationship between grip strength and patient disability as measured by the Katz independence scale (11). In addition, grip strength has been shown to be a good predictor of the patient's clinical condition (12). The measurement of grip strength, using a dedicated dynamometer, also has the advantage of being simple and reproducible (13) and has reference values adjusted for sex and BMI (14).

Gait speed is another indicator used to assess muscle function. It is associated with lower limb strength and is a predictor of disability and mobility limitation (7). Usual walking speed is most often measured over a distance of 4 or 6 m and has reference values adjusted for sex and height (12).

Dietitians also participate in the evaluation of muscle function by measuring body composition in terms of lean and fat mass. They perform bioelectrical impedanceometry, which allows estimation of body fat and lean mass volumes by measuring the resistance of biological tissues to a low-intensity, high-frequency sinusoidal electric current through electrodes (7). This measurement method is simple to use, inexpensive, reproducible and feasible in bedridden patients (7). It also correlates very well with MRI and reference values are obtained in various adult populations (15,16).

1.6 Research hypothesis

We hypothesize that muscle ultrasound is reliable and valid in the evaluation of muscle function during the screening of undernutrition in a population of hospitalized patients in diabetology-obesity, pneumology, oncology and gastro-nutrition, under 70 years of age.

2 Originality of the research

Ultrasound is a relatively simple and inexpensive tool compared to other methods of measuring body composition (DEXA or MRI) and provides additional information on muscle quantity and quality compared to the usual tools for measuring muscle function (Handgrip, functional tests). To our knowledge, no study has evaluated muscle ultrasound in the context of screening for undernutrition in a large patient population. On the one hand, this study will make it possible to evaluate the reliability and validity of ultrasound in the assessment of muscle deterioration during undernutrition and to propose threshold values of muscle function deterioration. On the other hand, it will provide information on the ultrasound characteristics of the muscle in the undernourished patient and their association with the prognosis of the patient.

3 Objective

3.1 Main objective

The main objective of this study is to evaluate the reliability and validity of muscle ultrasound in the context of screening for undernutrition in patients hospitalized in short-stay and follow-up care and rehabilitation of diabetology-obesity, pneumology, oncology and gastro-nutrition.

3.2 Secondary objectives

The secondary objectives will be, in patients hospitalized in short stay and follow-up care and rehabilitation of diabetes-obesity, pneumology, oncology and gastro-nutrition:

- Evaluate the correlation of muscle ultrasound with standard measures of muscle function;
- To compare the diagnostic capacity of muscle function assessment tools on undernutrition;

- Evaluate the association of muscle ultrasound measurements with patient morbidity and mortality:
 - Length of hospitalization;
 - Mortality rate;
 - Autonomy at discharge.

4 Judging criteria

4.1 Primary endpoint

The primary endpoint is the reduction in muscle mass measured by ultrasound thickness of the rectus femoris. The reduction in muscle mass measured by ultrasound will be used to estimate the diagnostic accuracy (sensitivity, specificity) of muscle ultrasound using bioelectrical impedance as the reference examination.

4.2 Secondary endpoint

Secondary endpoints will be:

- Correlation measurements of muscle ultrasound with:
 - Bioelectrical impedance;
 - Handgrip;
 - Walking speed.
- Comparison of the diagnostic accuracy in undernutrition of muscle ultrasound with those of :
 - Bioelectrical impedance;
 - Handgrip;
 - Walking speed.
- Measure of association of muscle ultrasound measurements with patient morbidity and mortality:
 - Length of hospitalization (days);
 - Mortality: proportion and date of occurrence of death among patients included during hospitalization;
 - Autonomy at discharge: Activities Daily Living (ADL) score, **Appendix 1**.

5 Eligibility Criteria

5.1 Inclusion criteria

Patients with the following criteria will be included:

- Admitted in short stay and follow-up care and rehabilitation of diabetology-obesity, pneumology, oncology and gastro-nutrition;
- Age between 18 and 70 years at inclusion;
- Affiliation with a social security system or beneficiary of such a system ;
- Oral, free, informed and express consent of the patient or his/her family member.

5.2 Non-inclusion criteria

Patients with the following criteria will not be included:

- Impossible to perform the ultrasound;
- Impossibility of performing bioelectrical impedancemetry ;
- Incapacity to consent;
- Patient refusal to participate in the study;
- Pregnancy (a pregnancy test should be performed if in doubt);
- Breastfeeding woman;
- Person subject to a safeguard of justice measure ;
- Patient under guardianship or curatorship;
- Patient in care limitation;
- Sampling in the ineligible study group.

5.3 Recruitment procedures

Patients will be recruited prospectively and consecutively within the short stay and follow-up care and rehabilitation services of diabetology-obesity, pneumology, oncology and gastro-nutrition of the Forcilles Hospital. The dietician of the unit identifies the patients upon admission to the service.

In 2020, according to PMSI data, 1128 patients under 70 years of age were hospitalized in our short-stay and follow-up care and rehabilitation services for diabetes-obesity, pneumology, oncology and gastro-nutrition. The monthly recruitment target is 6 patients, with a potential of 94 patients per month.

[figure not shown]
6 Research design

6.1 Type of study

This is a prospective, monocentric, interventional cohort study with minimal risks and constraints falling within the scope of Article L.1121-1 of the Public Health Code.

The research will be conducted in accordance with the protocol.

6.2 Research Diagram

6.3 Provisional research schedule

The duration of the recruitment will be 20 months with a follow-up of the patients during their entire hospitalization in the care unit, i.e. approximately 30 days (average length of stay), i.e. a total duration of the study estimated at 21 months.

- Submission to PPC: July 2022
- Start of inclusions: November 2022
- Duration of the inclusion period: 20 months
- Duration of participation for each patient: 30 days
- End of inclusions: July 2024
- Total duration of the research: 21 months
- Communication in congress: congress of medical societies of oncology, surgery, pneumology, nutrition and gastroenterology
- Publication: October 2024

6.4 Location of the study

The study will take place at the Forcilles Hospital, in the short stay and follow-up care and rehabilitation departments of diabetology-obesity, pneumology, oncology and gastro-nutrition.

7 Description of the usual care

7.1 Usual course of treatment

Patients admitted to short-stay and follow-up care and rehabilitation for diabetes-obesity, pneumology, oncology and gastro-nutrition benefit from medical, nursing and rehabilitation examinations and care. All of this care will not be modified within the framework of this protocol. Physiotherapists and dieticians provide their diagnostic assessment and rehabilitation on medical prescription. The EAPAs participate in the functional evaluation of the patient and carry out physical activities adapted to the patient, also on medical prescription.

As part of the screening for undernutrition in our establishment, the dieticians ensure a prospective and systematic collection of the patient's weight and its evolution over the last few months, of his BMI and an evaluation of the food intake, within 48 hours of the patient's admission to the service. The estimation of the patient's intake is done in collaboration with the nursing assistant.

The nurse's aide carried out a systematic measurement of grip strength when the patient was admitted to the ward ([Appendix 2](#)). A plan to train the nursing assistants to carry out this measurement has been set up by the physiotherapists.

The physical therapist or EAPA performs the measurement of the patient's walking speed routinely upon admission to one of these services ([Appendix 3](#)).

7.2 Standard evaluation procedures

7.2.1 Nutritional assessment

At the patient's admission, a dietetic evaluation is performed by the dietitian following the recommendations issued by the French Association of Dieticians-Nutritionists (AFDN) and the HAS. The dietitian collects all the data needed to detect malnutrition, such as weight, height, BMI, albumin level, and grip strength and walking speed (performed by the caregiver and the physiotherapist or the EAPA). The dietitian also looks for possible obstacles to feeding such as dental condition, swallowing problems or digestive discomfort.

The doctor looks for different pathologies impacting digestive absorption such as shortened or shortened stool syndromes, gastrectomies, pancreatic insufficiency etc. He also looks for factors of aggression such as cancers, chronic progressive diseases, infections etc.

All these data allow us to estimate the theoretical nutritional needs of the patient and to adapt the nutritional management. A follow-up of the ingestions is carried out by the dietician in collaboration with the nurses' aides.

7.2.2 Anthropometric measurements

When the patient is admitted, the ward's nurses and orderlies measure the patient's weight and height. When the patient can maintain the erect position, a conventional scale and a measuring rod are used for the measurements. If the patient cannot maintain this position, a weighing chair and a laser meter are used.

In order to evaluate the weight loss before hospitalization, the previous weight is sought in a hospitalization report or another recent medical document. A contact with the attending physician is also made in order to obtain information concerning the patient's weight follow-up. When this information is not available, the previous weight given by the patient is collected.

7.2.3 Biological measurements

On admission, a biological sample is usually taken from patients at risk of undernutrition in order to measure pre-albumin, albumin and C-reactive protein (CRP). These elements make it possible to determine the severity of undernutrition when it is present, according to the diagnostic criteria of the HAS.

7.2.4 Measurements of muscle function

Measurement of grip strength ("Handgrip")

The gripping force is evaluated with the Jamar® hydraulic force gauge by the caregiver.

The patient is in a sitting position, on a chair with a backrest, with his feet on the floor. The device is placed in the patient's hand. The patient is instructed to squeeze the dynamometer as hard as possible.

The measurement is made on the dominant side of the patient. The homolateral shoulder is in adduction (elbow to body), without extension or flexion and in neutral rotation. The elbow is flexed to 90° and in neutral prono-supination. The wrist is in neutral position. Three trials will be performed, and

the best value (in Kg) of the different tests is retained (see measurement procedure in [Appendix 2](#)).

Measurement of the walking speed ("Gait speed")

Walking speed (m/s) is measured on a 4-meter course, in a corridor, by the EAPA or the physiotherapist. The course is marked out on the ground. The course is marked out with markings on the ground and there are also 1-metre run-up and run-down zones. The patient is instructed to walk the course at a normal speed and not to complete the distance as quickly as possible. The course is completed 3 times and the best time (in seconds) is recorded (see procedure in [Appendix 3](#)).

7.3 Definition of undernutrition

Undernutrition is defined according to the GLIM diagnostic method:

Phenotypic criteria			Etiological criteria	
Weight loss (%)	Low BMI (kg/m ²)	Reduction in muscle mass	Reduction of food intake or absorption	Inflammatory situation
> 5% in the last 6 months or > 10% beyond 6 months	< 20	Reduction evaluated by a validated measurement technique*.	≤ 50% of food intake > 1 week or any reduction > 2 weeks, or any gastrointestinal pathologies or symptoms impacting assimilation or absorption	Acute pathologies or certain chronic or malignant pathologies

The diagnosis of undernutrition is positive if an etiological and a phenotypic criterion are present. This assessment will be preceded by a MNA-SF ([Appendix 4](#)). The methods for measuring the reduction in muscle mass are described in section "**7.2.4. Measurement of muscle function**".

Among patients with undernutrition, severe undernutrition is defined as:

Moderate undernutrition	Severe undernutrition

 • BMI < 20 kg/m² • Weight loss of 5-10% in the last 6 months or 10-20% after 6 months • Mild to moderate reduction in muscle mass 	
 • BMI < 18.5 kg/m² • Weight loss of >10% in the last 6 months or >20% beyond 6 months • Severe reduction in muscle mass

The prevalence of undernutrition was defined as the proportion of patients with moderate and/or severe undernutrition among the patients included in the study.

8 Evaluation procedure added by the research

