1.2 International consensus on the definition of undernutrition

In 2019, the Global Leadership Initiative on Malnutrition (GLIM) published an international consensus report on diagnostic criteria for undernutrition (1). The diagnostic criteria are numerous, and include etiological criteria such as reduced food intake; an inflammatory context; symptoms such as anorexia, fatigue; phenotypic criteria such as weight loss, body mass index (BMI), fat to lean mass ratio, fluid retention, and muscle function. GLIM has chosen to select the most relevant criteria among the etiological and phenotypic criteria:

- Etiological criteria: reduced food intake and inflammatory state of the patient;
- Phenotypic criteria: weight loss, BMI, and reduced muscle mass. The presence of at least one etiological criterion and one phenotypic criterion is mandatory to make the diagnosis of undernutrition (Table 1).

Table 1: Diagnostic criteria for undernutrition

Phenotypic criteria			Etiological criteria	
Weight loss (%)	Low BMI (kg/m ²) ²	Reduction in muscle mass	Reduction of food intake or absorption	Inflammatory situation
> 5% in the last 6 months or > 10% beyond 6 months	< 20	Reduction evaluated by a validated measurement technique*.	≤ 50% of food intake > 1 week or any reduction > 2 weeks, or any gastrointestinal pathologies or symptoms impacting assimilation or absorption	Acute pathologies or certain chronic or malignant pathologies
≥ 5% in 1 month or ≥ 10% in 6 months or loss ≥ 10% from usual weight prior to start of the disease	< 18,5	Quantified Reduction* * (QR)	Same as	Same as

* Suggested methods of measuring muscle mass: Dual X-ray Absorptiometry (DEXA); bioelectrical impedance; CT or MRI. In the absence of these tools, anthropometric measurements such as arm or leg circumference can be used. Grip strength measurement is considered a complementary measure. The threshold values are those of Cruz et al (7).

** Methods of measuring muscle mass proposed by the HAS:

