Muscle mass is described as a major diagnostic criterion, since it is on the one hand a direct indicator of protein catabolism related to undernutrition, but also a reflection of functional impairment in the patient, as it is directly associated with functional capacities, autonomy and prognosis (1). Different measurement tools are suggested, such as bioelectrical impedance, ultrasound or magnetic resonance imaging, leaving the choice of tool to the clinicians, depending on experience and local resources. Handgrip measurement is considered a complementary measure.

GLIM recommends an assessment of the risk of undernutrition, using validated questionnaires such as the NRS (Nutritional Risk Screening) or the MNA-SF (Mini Nutritional Assessment-Short Form). The degree of severity of undernutrition is only assessed on the basis of phenotypic criteria.

The severity of undernutrition can then be determined (Table 2).

Table 2: Classification of the severity of undernutrition

Moderate undernutrition	Severe undernutrition

 • BMI < 20 kg/m² • Weight loss of 5-10% in the last 6 months or 10-20% beyond 6 months • Mild to moderate reduction in muscle mass 	
 • BMI < 18.5 kg/m² • Weight loss of >10% in the last 6 months or >20% beyond 6 months • Severe reduction in muscle mass

 • 17 < BMI < 18.5 kg/m² • Weight loss \geq 5% in 1 month or \geq 10% in 6 months or loss \geq 10% from usual weight before onset of illness • Measurement of albumin by immuno-electrometry or immunoturbidimetry > 30 g/L and < 35 g/L. 	
 • BMI < 17 kg/m² • Weight loss \geq 10% in 1 month or \geq 15% in 6 months or loss \geq 15% from usual weight before onset of disease • Measurement of albumin levels by immuno-electrometry or immunoturbidimetry < 30 g/L

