10.5.2 Compare the diagnostic capacity of muscle function assessment tools on undernutrition

The diagnostic capabilities of the different tools for measuring muscle function (Handgrip, gait speed, bioelectrical impedance and muscle ultrasound) will be compared by ROC curves.

10.5.3 Evaluate the association of muscle ultrasound measurements with patient morbidity and mortality

Morbidity and mortality will be compared between the groups with and without ultrasound-determined muscle function impairment, comparing length of hospital stay, mortality, and independence at discharge.

Length of hospitalization

There is a relationship between the incidence of mortality and all of the length of stay variables. Length of stay will therefore be analyzed using a competitive risk method, which takes into account the fact that patients who die are no longer eligible for length of stay analysis (26). The estimator also provides the probability of in-hospital death, so the probability of hospital discharge versus death at any time after study inclusion can be assessed simultaneously.

Mortality rate

The estimation of mortality rates will be performed by the Kaplan and Meier method. Comparison of the 2 curves will be performed by a Logrank test. The mortality rates in the 2 groups will be estimated via the survival curves.

ADL

The ADL score will be compared between the 2 groups using the discrete numerical variable comparison tests described in the general aspects.

11 Expected results in terms of scientific and professional advances

The results of this study will make it possible to verify whether ultrasound is a reliable and valid tool in the evaluation of peripheral muscle function in the context of screening for undernutrition. On the other hand, they will allow us to propose threshold values for the alteration of muscle function and to provide information on the ultrasound characteristics of the muscle in the undernourished patient and their association with the prognosis of the patient. The different tools could lead to a different estimation of the reduction of muscle mass and therefore a different prevalence of undernutrition. The results of our study will help to evaluate this and to guide professionals in the choice of tools to assess muscle function.

12 Expected benefits and risks for patients

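### The secondary ROC comparison for undernutrition is open to incorporation bias: the GLIM label can rest on one of the four compared tools, and the protocol does not settle which one

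*Combined protocol and SAP*

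**What the plan says.** - **Comparison.** The secondary endpoint in 4.2 is "Comparison of the diagnostic accuracy in undernutrition of muscle ultrasound with those of" impedance, handgrip and walking speed. Section 10.5.2 says that the tools ("Handgrip, gait speed, bioelectrical impedance and muscle ultrasound) will be compared by ROC curves". The target in its heading is undernutrition; its text names no reference standard.
- **Label.** Section 7.3 adopts GLIM: "The diagnosis of undernutrition is positive if an etiological and a phenotypic criterion are present". Reduced muscle mass is one of the three phenotypic criteria, beside weight loss and BMI below 20, so it can supply the phenotypic part alone.
- **How muscle mass is measured, first answer.** Section 7.3: "The methods for measuring the reduction in muscle mass are described in section" 7.2.4. That section holds the handgrip and gait-speed procedures, without cut-offs.
- **Second answer.** The footnote to Table 1 in 1.2: "Suggested methods of measuring muscle mass: Dual X-ray Absorptiometry (DEXA); bioelectrical impedance; CT or MRI". It adds: "Grip strength measurement is considered a complementary measure". Sections 8.2 and 10.4 give impedance cut-offs of 7 and 5.7 kg/m² for men and women.
- **Availability.** Section 12.1 has impedance done systematically in included patients, and 5.2 excludes patients in whom it is impossible. The data lists in 9.2 and 9.5 contain no DEXA, CT, MRI or limb circumference.

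**The concern.** A patient with an etiological criterion and low muscle mass, but no weight loss and a normal BMI, is labelled undernourished solely because of the tool that measured muscle mass. That tool is then scored against a label it helped to create, and it gains AUC over an equally valid tool that is not in the label. Blinding the operators (8.2, 8.3.2) does not prevent this, because the overlap lies in how the label is built.

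Section 11 wants the results to guide professionals in choosing a tool, and it acknowledges that the tool may change the prevalence of undernutrition. As the text stands, neither the measurement behind the reported prevalence nor the comparison that is biased is fixed before the data are seen.

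**Working it through.** **1. Which tools can enter the label.** Of the methods named for muscle mass in 1.2 and 7.3, the study collects only impedance, handgrip, gait speed and ultrasound (9.2). All four are compared in 10.5.2, so whichever one sets the criterion is embedded.

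**2. The plan's own figures.** No figure in the plan concerns 10.5.2. The total of 118 comes from the reproducibility calculation in 10.1 (ρ1 = 0.8, ρ0 = 0.70, k = 2, power 80%). With θ = ρ/(1−ρ), θ0 = 2.333 and θ1 = 4, so C0 = (1 + 2×2.333)/(1 + 2×4) = 0.6296 and (ln C0)² = 0.214. Then n = 1 + 2×(1.645 + 0.842)²×2/0.214 ≈ 117 at one-sided 5%, which agrees closely with 118.

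**3. Agreement implied by 10.1.** The plan expects ultrasound to have sensitivity 90% and specificity 85% against impedance, with impairment in 45-60%.
- At 45%: both positive 0.45×0.90 = 0.405; ultrasound positive 0.405 + 0.55×0.15 = 0.4875.
- At 60%: both positive 0.54; ultrasound positive 0.54 + 0.40×0.15 = 0.60.
- The bivariate normal correlation that gives these cells is 0.925 in both cases.

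**4. Illustrative model.** Each tool = √s·T + √(1−s)·error, where T is true muscle status. The four tools are equally valid and their errors independent, so s is the correlation between any two tools. From the protocol: muscle criterion positive in 45% or 60%, n = 118. Assumed, because the documents do not say:
- weight loss or low BMI in 20% or 35%, with latent correlation to T of 0, 0.3 or 0.5;
- an etiological criterion in 70% or 90%, independent of the rest.

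The label is etiological AND (weight loss/BMI OR low muscle).

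**5. One setting by hand.** Take 45%, 20% and 70%, with weight loss/BMI unrelated to T. Full GLIM: 118×0.70×(1 − 0.55×0.80) = 118×0.392 = 46.3 cases. Cases with weight loss or low BMI: 118×0.70×0.20 = 16.5. The other 29.8 (64%) are labelled by the muscle tool alone. Over the grid with s of 0.4-0.8 this share is 39-71%, and full GLIM gives 42-79 cases.

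**6. AUC lead of the embedded tool over ultrasound, full GLIM label.**

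| Agreement between tools | Impedance embedded | Handgrip/gait speed embedded (handgrip lead) |
|---|---|---|
| s = 0.925, as 10.1 implies | about 0.02-0.03 | about 0.01-0.02 |
| s = 0.4 to 0.8 | about 0.05-0.24 | about 0.02-0.14 |

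The handgrip column covers four ways of combining it with gait speed. In that column, impedance minus ultrasound stays near 0, because neither is in the label. With the muscle criterion removed, all gaps are near 0, provided the tools' errors are unrelated to BMI.

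**7. Shared error.** If tool errors are correlated at 0.5, s of 0.4-0.8 becomes an effective correlation of 0.4 + 0.6×0.5 = 0.70 to 0.8 + 0.2×0.5 = 0.90. The impedance gap falls to about 0.03-0.13.

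**The case against.** The strongest reply is that the ambiguity is only a wrong cross-reference. Impedance is measured in every participant, appears in the Table 1 footnote and has cut-offs. Handgrip and gait speed have none, and they measure function rather than mass, so 7.3 cannot be carried out as written. This stands: a slip is the likeliest explanation. It does not remove the bias, since an impedance-based label embeds impedance, which is also compared.

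A second reply is that the effect may be small. This also stands in part. A reader might infer from the weak-agreement range that the ranking is badly distorted. The only agreement figure in the documents implies a correlation of 0.925. At s of 0.4-0.8, ultrasound with 85% specificity would reach only about 36-74% sensitivity against impedance, far below the plan's expectation. Yet 90% and 85% are planning values, not results, so weaker agreement cannot be excluded.

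Third, 7.3 places an MNA-SF before the GLIM assessment, and 8.1 sends at-risk and undernourished patients on to it. If this is a gate, some patients with isolated low muscle mass would never receive the label. That was not modelled and could change the gaps.

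Finally, one might infer from 1.2 ("Different measurement tools are suggested, such as bioelectrical impedance, ultrasound or magnetic resonance imaging, leaving the choice of tool to the clinicians") that ultrasound could set the criterion and be favoured. That sentence is background on GLIM; no study procedure assigns ultrasound this role.

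**Conclusion.** The point holds for the secondary comparison in 4.2 and 10.5.2. The reference label can contain a compared tool, the passages disagree on which, and on either reading the embedded tool gains AUC over ultrasound by construction.

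The size is unknown, because the documents do not give the share of patients labelled by muscle mass alone. Under the stated assumptions, the impedance lead is about 0.02-0.03 if agreement is as 10.1 expects and about 0.05-0.24 if it is weaker. The handgrip lead is about 0.01-0.02 and 0.02-0.14 respectively. Shared error would reduce the gaps.

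Two stronger readings are not supported. The primary analysis is not affected in this way: 4.1 and 10.4 assess ultrasound against impedance, with ultrasound outside the reference. Nor is every pairwise comparison biased: if handgrip and gait speed set the criterion, impedance against ultrasound is untouched.

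**What to change.** 1. The sponsor should reconcile 7.3, 7.2.4, the Table 1 footnote, 8.2 and 10.4. It should state which measurement sets the muscle-mass criterion, the reported prevalence and the reference for 10.5.2.
2. In 10.5.2, report the four-tool ROC comparison against full GLIM and, beside it, against GLIM without the muscle-mass criterion (an etiological criterion plus weight loss or BMI below 20, as in 7.3). Flag the full-GLIM AUC of any embedded tool as subject to incorporation bias, and do not rank that tool on it alone. Full GLIM should stay, since 1.2 notes that "Muscle mass is described as a major diagnostic criterion".

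**Cost.** Weight history, BMI and the etiological criteria are already collected (9.2), and 118 does not change. The work is a wording change and one more set of ROC analyses; it goes to the ethics committee if judged substantial (14.5).

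**Downsides.** Under the assumptions, the muscle-free label leaves about 16-37 cases (118×0.20×0.70 = 16.5 to 118×0.35×0.90 = 37.2). At s of 0.4-0.8, the 95% half-width of an AUC difference becomes about 0.07-0.17, against 0.06-0.12 with full GLIM. The label removes direct incorporation only. Impedance indices are in kg/m² and may share dependence with BMI. With an assumed error correlation of 0.1 or 0.3, impedance would still lead ultrasound on this label by about 0.02-0.04 or 0.05-0.11 (same range of s). If handgrip and gait speed set the criterion, the muscle-free label does not improve impedance against ultrasound and could worsen it. For these reasons it belongs beside full GLIM, not in its place.

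The difference between the muscle mass index in 8.2 and the appendicular index in 10.4 concerns the primary reference and should be raised separately.
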